7. Deviations with regard to vaccine preparation or administration.

Protocol violations leading to exclusion from the Immunogenicity Analysis Set will be reviewed on an ongoing basis, including reviews of the case report form data and protocol deviations as stored in the clinical trials management system. The final list of exclusions from the Immunogenicity Analysis Set will be approved at a data review meeting prior to the primary analysis reporting.

The following analysis sets will be used to obtain estimates of the primary and secondary estimands defined in the protocol, additional immunogenicity endpoints, and safety endpoints.

Table 2 Analysis Sets by Objective

Objectives	Analysis Sets
Analysis set for the primary estimand, supportive immunogenicity, and exploratory objectives	Immunogenicity Analysis Set Sensitivity for primary estimand: Safety Analysis Set with at least one post-baseline neutralizing titer, regardless of protocol deviations substantially affecting immunogenicity outcomes
Analysis set for secondary estimands and additional safety endpoints	Safety Analysis Set

4 Statistical Analyses

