4.2.3.1 Sensitivity using the Safety Analysis Set

The analytical approach used for the primary estimand will be repeated using the Safety Analysis Set including any available post-last vaccination value for the primary time point (2 weeks post-last vaccination) regardless of window, and without respect to protocol deviations that may substantially affect immunogenicity outcomes. If multiple post-last vaccination neutralizing titer values are available, the value closest to the target day (2 weeks post last vaccination, i.e., Week 6 for Group 1 and Week 2 for Group 2 and Group 3) will be used for the sensitivity analysis. If two values are equidistant from the target day, the later value will be used. No pre-vaccination titer values will be analyzed as post vaccination titer results.

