4.2.3.2 Sensitivity using Multiple Imputation for the Safety Analysis Set

Because the window between vaccination and the primary endpoint measurement is short, the number of subjects with missing data due to intercurrent events or protocol deviations substantially affecting the immunogenicity results is expected to be small. If data are missing despite the short window, missing values will be imputed via the multiple imputation (MI) method as a sensitivity analysis using the Safety Analysis Set. Missing values will be assumed to be missing at random, such that the reason for the missing value is not dependent on the result itself. As the MI procedure will be performed on the Safety Analysis Set, regardless of protocol deviations, post vaccination neutralizing titers that are out of window will be included rather than imputing a “missing” value for full accounting of the available data. Inclusion of out of window titer results will follow the method used for the Sensitivity Analysis using the Safety Analysis Set.

The multiple imputation sensitivity analyses will be performed separately for each group due to the different background characteristic of the two populations. Although analyses for Groups 2 and 3 are based on the fold-increase from baseline neutralizing titers, imputation of missing data will be performed at the neutralizing titer level, with fold-increase computed after imputation.

Group 1 Multiple Imputation Procedure

For Group 1, assuming the post-vaccination \log_{10} titer values are normally distributed, MI will be used to create 100 complete data sets that will account for the random variability in the \log_{10} neutralizing titer values. Week 2, Week 4, and Week 5 \log_{10} neutralizing titer results, number of vaccinations received, year of birth, sex, and race will be used in the joint model to predict the \log_{10} neutralizing titer value for the primary estimand time point at Week 6.

Qualitative tests for SARS-CoV-2 antibodies are required for inclusion in the trial and appropriate placement of subjects into their respective seronegative or seropositive groups. As Group 1 subjects are required to be seronegative at screening, most Baseline neutralizing titers are expected to be below the LLOQ. As this would provide little information to the joint distribution from which to draw the MI samples, Baseline neutralizing titer values will not be included in the Group 1 MI procedure.

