For Groups 2 and 3, again assuming the \log_{10} titer values are normally distributed, MI will be used to create 100 complete data sets that will account for the random variability in the neutralizing titer values. Group 2 and 3 analyses will be performed separately, but using the same method. Baseline and Week 1 \log_{10} neutralizing titer values, stratification subgroup, year of birth, sex, and race will be used in the joint model to predict the \log_{10} neutralizing titer value for the primary estimand time point at Week 2. Qualitative tests for SARS-CoV-2 antibodies are required for inclusion in the trial and appropriate placement of subjects into their respective seronegative or seropositive groups. However, the chance for missing Baseline neutralizing titer values still exists. In addition, as the missing pattern of titer values may not be monotone, i.e., subjects may be missing Baseline neutralizing titer values, Week 1, or Week 2 neutralizing titer values, or a combination of these values, a FCS model will be used, assuming the existence of a joint distribution for all variables used to predict the missing values and allowing the Baseline and Week 1 \log_{10} titer results to be imputed, if needed, to inform the missing Week 2 neutralizing \log_{10} titer result.

For missing Baseline and Week 1 neutralizing titer values in Groups 2 and 3, titer results can still be assumed log-normally distributed. Using the FCS regression model, missing neutralization titer results will be imputed using the simulated from the posterior predictive distribution of the parameters Baseline and Week 1 \log_{10} neutralizing titers, stratification subgroup, year of birth, sex, and race.

After the creation of the 100 complete datasets, the fold-increase for Week 2 versus Baseline neutralizing titer results, i.e., the difference in the values on the \log_{10} scale, will be created for all Safety Analysis Set subjects. The mean difference in \log_{10} titers from Baseline to Week 2 and corresponding standard errors will be calculated within each imputation, and combined over the 100 imputations. The combined results will be presented on the \log_{10} scale using means and 95% CIs, as well as back transformed to present the geometric mean fold-increases and associated 95% CIs on the original scale.

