^g Any serum blood or PBMC samples must be taken before vaccination

^h If symptoms persist at Day 8, daily symptoms and temperature will continue to be measured and documented each day until resolved

Appendix 3: Schedule of Events for Groups 2 and 3

Visit (V)	SCR	V1	V2	V3	V4/ EAP	FU1	FU2	FU3	FU4
Day / Visit +... Days	-14--1	1	V1 +7-10	V1 +12-16	V1 +28-35	V1 +91- 105	V1 +181- 195	V1 +361- 375	V1 +722- 736
Target week	-2	0	1	2	4	13	26	52	104
Informed consent	X								
Check incl./excl. criteria	X	X							
Medical History	X								
Complete physical exam ^a (body height and weight, BMI assessment)	X								
Evaluation of vital signs ^a	X	X	X	X	X	X			
Targeted physical exam incl. auscultation of the heart and lung ^a		X	X	X	X	X			
ECG ^a	X								
Recording of prior and concomitant medication	X	X	X	X	X	X			
Counseling on avoidance of pregnancy for WOCBP ^b	X	X							
AE/SAE/AESI recording		X	X	X	X	X ^c	X ^c	X ^c	X ^c
Pregnancy test for WOCBP ^d	X	X			X				
Obtaining blood for safety lab ^a	X			X	X ^e				
SARS-CoV-2 specific antibody test	X								
SARS-CoV- 2 infection test (PCR)	X		(X) ^f	(X) ^f	(X) ^f	(X) ^f	(X) ^f	(X) ^f	(X) ^f
Hep-B, HCV, HIV test	X								
Serum collection for antibody testing ^f		X	X	X	X	X	X	X	X
Collection of PBMC ^g		X	X						
Vaccine administration & subject observation (≥30 minutes)		X							
Recording of immediate AEs		X							
Handout of memory aid		X							
Collection of memory aid ^h			X						
Examination of injection site			X						

Abbreviations: AE = adverse event; AESI = adverse event of special interest; BMI = body mass index; EAP = end of active phase visit; ECG = electrocardiogram; FU = follow-up; Hep-B = hepatitis-B, HCV = hepatitis C virus; HIV = human immune deficiency virus; PBMC = peripheral blood mononuclear cells; SAE = serious adverse event; SARS-CoV-2 = severe acute respiratory syndrome coronavirus 2; SCR = Screening; WOCBP = woman of childbearing potential.

X: mandatory; (X): if indicated/if applicable

^a If clinically indicated, additional safety measures can be taken at any other trial visits or at unscheduled visits.

In addition, auscultation of the heart and lungs will be performed to check specifically for signs of any heart condition or respiratory disorders.

^b Review of acceptable contraceptive methods and recent menstrual history with WOCBP

^c Only SAEs/AESIs will be collected during the follow-up period (FU1-FU4)

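### The sensitivity rule for the 2-week titer has no outer limit, so it most naturally lets 1-week titers stand in for 2-week titers and stops the imputation model from using its own 1-week predictor

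*SAP*

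**What the plan says.** The observed-case sensitivity analysis (SAP 4.2.3.1) uses the Safety Analysis Set, "including any available post-last vaccination value for the primary time point (2 weeks post-last vaccination) regardless of window". Where a subject has several values the choice is by distance: "If multiple post-last vaccination neutralizing titer values are available, the value closest to the target day" is taken, the target being Week 6 in Group 1 and Week 2 in Groups 2 and 3. There is a tie rule: "If two values are equidistant from the target day, the later value will be used". The section closes by barring pre-vaccination titers. SAP Section 3, Table 2 describes the set as "Safety Analysis Set with at least one post-baseline neutralizing titer". No text limits how far from the target day a value may lie.

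The MI analysis (SAP 4.2.3.2) adopts the same selection: "Inclusion of out of window titer results will follow the method used for the Sensitivity Analysis using the Safety Analysis Set". It also gives substitution precedence, since "post vaccination neutralizing titers that are out of window will be included rather than imputing a" missing value. Its models then use the 1-week titer as a predictor: Week 5 for Week 6 in Group 1, and Week 1 for Week 2 in Groups 2 and 3, "allowing the Baseline and Week 1 \log_{10} titer results to be imputed, if needed, to inform the missing Week 2 neutralizing \log_{10} titer result".

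The row "Serum collection for antibody testing" in SAP Appendices 2 and 3 shows serum drawn, counting from the last vaccination, at +7 to +10, +12 to +16, +28 to +35 and +91 to +105 days. Groups 2 and 3 have later draws as well.

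**The concern.** The endpoint is the titer 2 weeks after the last vaccination, and SAP 1.1 frames the primary question as one about peak titers. A 1-week or 4-week titer is a different quantity. A rule that picks the nearest sample from any visit puts such values into the 2-week mean as if they were measured 2-week titers, with no allowance for the difference.

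The second consequence concerns MI. Its strongest source of information on a missed 2-week sample is the titer drawn a few days earlier. If that titer has already been moved into the 2-week slot, nothing is left to impute for that subject. The same number then appears in the regression as both predictor and outcome, which pulls the fitted relation towards equality for the subjects who are imputed. Both sensitivity analyses also carry the same substituted values, so agreement between them says little about how missed 2-week samples affect the result.

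**Working it through.** **Step 1. The plan's own yardstick.** SAP Section 6 assumes an SD of 0.5 log10 before and after the booster and a correlation of 0.3.

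- SD of the log10 difference = √(0.25 + 0.25 − 2 × 0.3 × 0.25) = 0.5916.
- Half-width at n = 90: 1.96 × 0.5916 / √90 = 0.122, as stated. At a ratio of 4 the interval is 3.02 to 5.30 (stated 3.0 to 5.3).
- Half-width for Group 1, n = 30: 1.96 × 0.5 / √30 = 0.179, as stated.

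**Step 2. Which sample the rule picks.** Distance of each scheduled draw from day +14 after the last vaccination:

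| Draw | Window (days) | Distance from +14 |
|---|---|---|
| 1-week (V2; V5 in Group 1) | +7 to +10 | 4 to 7 |
| 2-week (V3; V6 in Group 1) | +12 to +16 | 0 to 2 |
| 4-week (V4; V7 in Group 1) | +28 to +35 | 14 to 21 |
| 3-month (FU1) | +91 to +105 | 77 to 91 |

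An in-window 2-week sample always wins. If it is absent, the 1-week value is taken, then the 4-week value. A late 2-week sample can also lose. A 1-week sample on day +10 is 4 days from target, so it displaces a 2-week sample drawn after day +18. At exactly +18 the tie rule keeps the later one. For a 1-week sample on day +7 the switch comes after day +21.

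**Step 3. What is left for MI.** A Week 2 or Week 6 value is imputed only if the subject has no post-last-vaccination titer in the data. Such a subject has no Week 1 or Week 5 titer either, so the number of subjects in whom an observed 1-week titer informs an imputed 2-week titer is zero by construction.

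For scale, assume that 90 subjects each miss each visit independently with probability 5%. The documents give no rate.

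- Missing 2-week values: 90 × 0.05 = 4.5.
- Filled by the 1-week value: 4.5 × 0.95 = 4.28.
- Filled by the 4-week value: 4.5 × 0.05 × 0.95 = 0.21.
- No sample through 4 weeks: 90 × 0.05³ = 0.01.

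If other visits' samples did not qualify, all 4.5 would be imputed. For visit-miss rates of 2% to 10% the comparison is 1.8 to 9.0 imputed against 0.001 to 0.09. If a further 2% of subjects have no post-vaccination sample at all, then at 5% per visit it is 90 × (0.02 + 0.98 × 0.05) = 6.2 against 90 × (0.02 + 0.98 × 0.05³) = 1.8.

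**Step 4. Size of the shift.** With k substituted values lying d log10 below the true 2-week titer, the group mean moves by k × d / n. Both k and d are assumptions.

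| n | k | d | Shift (log10) | Estimate | Share of half-width |
|---|---|---|---|---|---|
| 90 | 5 | 0.2 | 0.011 | 4.0 → 3.90 | 9% |
| 90 | 5 | 0.4 | 0.022 | 4.0 → 3.80 | 18% |
| 90 | 9 | 0.2 | 0.020 | 4.0 → 3.82 | 16% |
| 90 | 9 | 0.4 | 0.040 | 4.0 → 3.65 | 33% |
| 30 | 3 | 0.4 | 0.040 | 200 → 182 | 22% |

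**The case against.** The best defence is a narrower reading. The rule speaks of a value for the primary time point, which could mean only the V3 or V6 sample, taken early, late or repeated. SAP 4.1.3 sends out-of-window samples to 4.2.3.1, and the third listed exclusion in SAP Section 3 is about the 2-week sample being out of window. The MI models expect Week 2 or Week 6 to be missing while the 1-week titer is present. On that reading there is no substitution across visits.

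This has force, but the rest of the text points the other way. The closest-value and tie rules, and the bar on pre-vaccination titers, presuppose candidates from several draws. Table 2 asks for one post-baseline titer, not a 2-week titer. SAP 4.2.4 states that its by-visit summaries involve no windowing, which suggests that this analysis does. If the narrow reading is meant, the SAP still has to say so.

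Two further points stand. SAP 4.2.4 already gives by-visit titer summaries for both analysis sets, so an unsubstituted 2-week geometric mean titer for the Safety Analysis Set will be available beside the sensitivity result, although fold increases are not named there. Keeping out-of-window values is also a declared choice, and a late V3 or V6 sample can reasonably be kept.

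A reader might infer that MI is left with nothing to do. The documents do not support that. SAP Appendix 1 defines the last vaccination in Group 1 as the second dose, so a one-dose subject has no post-last-vaccination titer but may have Week 2 and Week 4 titers, which the model uses with the number of doses. In Groups 2 and 3, MI also fills missing baselines, which SAP 4.1.1 drops from the observed-case ratios. Subjects with no post-last-vaccination titer are imputed as well.

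**Conclusion.** The point holds as a defect in a stated rule, limited to the two sensitivity analyses. On its most natural reading, 4.2.3.1 puts 1-week and occasionally 4-week titers into a 2-week endpoint. By importing that rule, 4.2.3.2 prevents the Week 1 or Week 5 titer from ever informing a missing endpoint, contrary to the model's stated purpose. In subjects given their 1-week value, that value is both predictor and outcome. The primary analysis, in the Immunogenicity Analysis Set, is unaffected, and no hypothesis is tested.

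The numerical effect is modest: 0.011 to 0.040 log10 at n = 90, or about 9% to 33% of the planned half-width. It rests on assumed counts (5 to 9 of 90) and an assumed titer gap (0.2 to 0.4 log10). The documents give neither, and SAP 4.2.3.2 expects few missing values.

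Two stronger inferences should be resisted. One is that 3-month titers would commonly be used. That needs the 1-, 2- and 4-week samples all to be missing, about 0.01 of 90 subjects at an independent 5% per visit. SAP 4.6 also runs the Groups 2 and 3 primary-estimand analyses on data cleaned through the +28 to +35 day visit. The other is that the rule manufactures robustness. Under the assumptions above, substitution moves the sensitivity estimate away from a primary value of 4.0, so the primary result would look less robust. What can be said is that the two sensitivity analyses share the same substituted values and are not independent checks on missed samples.

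**What to change.** In SAP 4.2.3.1, state that the 2-week value may come only from the nominal V3 sample (Groups 2 and 3) or V6 sample (Group 1), whatever its actual day, or from an unscheduled sample nearer to that visit window than to any other scheduled serum visit. Otherwise the value is missing. The closest-day and tie rules can stay for choosing among qualifying samples.

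In SAP 4.2.3.2, state that a value missing under this definition is imputed with the MI model already specified, so that the Week 1 or Week 5 titer does the work intended for it.

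The cost is two sentences and a small programming change, with no new data. The observed-case sensitivity analysis loses the few subjects without a 2-week sample, and the MI analysis recovers them under its missing-at-random assumption. Adding the Week 4 (Groups 2 and 3) or Week 8 (Group 1) titer as a further predictor is optional. It corrects no error and depends on those results being available at the time of analysis.

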4.2.3.2 Sensitivity using Multiple Imputation for the Safety Analysis Set

Because the window between vaccination and the primary endpoint measurement is short, the number of subjects with missing data due to intercurrent events or protocol deviations substantially affecting the immunogenicity results is expected to be small. If data are missing despite the short window, missing values will be imputed via the multiple imputation (MI) method as a sensitivity analysis using the Safety Analysis Set. Missing values will be assumed to be missing at random, such that the reason for the missing value is not dependent on the result itself. As the MI procedure will be performed on the Safety Analysis Set, regardless of protocol deviations, post vaccination neutralizing titers that are out of window will be included rather than imputing a “missing” value for full accounting of the available data. Inclusion of out of window titer results will follow the method used for the Sensitivity Analysis using the Safety Analysis Set.

The multiple imputation sensitivity analyses will be performed separately for each group due to the different background characteristic of the two populations. Although analyses for Groups 2 and 3 are based on the fold-increase from baseline neutralizing titers, imputation of missing data will be performed at the neutralizing titer level, with fold-increase computed after imputation.

Group 1 Multiple Imputation Procedure

For Group 1, assuming the post-vaccination \log_{10} titer values are normally distributed, MI will be used to create 100 complete data sets that will account for the random variability in the \log_{10} neutralizing titer values. Week 2, Week 4, and Week 5 \log_{10} neutralizing titer results, number of vaccinations received, year of birth, sex, and race will be used in the joint model to predict the \log_{10} neutralizing titer value for the primary estimand time point at Week 6.

Qualitative tests for SARS-CoV-2 antibodies are required for inclusion in the trial and appropriate placement of subjects into their respective seronegative or seropositive groups. As Group 1 subjects are required to be seronegative at screening, most Baseline neutralizing titers are expected to be below the LLOQ. As this would provide little information to the joint distribution from which to draw the MI samples, Baseline neutralizing titer values will not be included in the Group 1 MI procedure.

In addition, as the missing pattern of titer values may not be monotone, i.e., subjects may be missing Week 2, Week 4, Week 5, or Week 6 neutralizing titer results, or a combination of these values, a fully conditional specification (FCS) method will be used. This method assumes the existence of a joint distribution for all variables used to predict the missing values and allows Week 2, Week 4, and Week 5 \log_{10} titer value to be imputed, if needed, to inform the missing Week 6 neutralizing titer values.

MI analyses will be performed in SAS using the PROC MI and PROC MIANALYZE procedures. A minimum of \log_{10} of half of the LLOQ will be set for imputed values to correspond to the observed data range. In addition, a seed of 19201 will be used for the procedure. The following is the sample code for the MI sensitivity analyses of the primary estimand for Group 1.

titersl: the dataset containing the \log_{10} neutralizing titer data along with the covariates used in the analysis, one record per subject.

sex: The sex identifier

yob: Year of birth

race: The race identifier

nvacc: Number of vaccinations received (1 vs. 2)

ltiterW2: \log_{10} Week 2 Titer Result

ltiterW4: \log_{10} Week 4 Titer Result

ltiterW5: \log_{10} Week 5 Titer Result

ltiterW6: \log_{10} Week 6 Titer Result

```

proc mi data=titersl out=titermi n impute=100 seed=19201 minimum=[log10LLOQ/2];
  class nvacc sex race;
  var nvacc yob sex race ltiterW2 ltiterW4 ltiterW5;
  fcs nbiter=20 reg(ltiterW6 = ltiterW2 ltiterW4 ltiterW5 nvacc yob sex race
    /details);
run;

proc means data=titermi n oprint nway;
  by _imputation_;
  var ltiterW6;
  output out=summ(drop=_type_ _freq_) n=n mean=logmn stderr=logse;
run;

ods output parameterestimates=grouplest;
proc mianalyze data=summ;
  modeleffects logmn;
  stderr logse;
run;
data grouplest2;
  set grouplest;
  GMT=10**estimate;
  GMT_LCL=10**LCLmean;
  GMT_UCL=10**UCLMean;
  keep estimate lclmean uclmean gmt:;
  label estimate='Mean Log10 Titers'
    lclmean='Lower 95% CI of the Mean Log10 Titers'
    uclmean='Upper 95% CI of the Mean Log10 Titers'
    gmt='Geometric Mean Titer'
    GMT_LCL='Lower 95% CI of the Geometric Mean Titer'
    GMT_UCL='Upper 95% CI of the Geometric Mean Titer'
run;

```

Groups 2 and 3 Multiple Imputation Procedure

For Groups 2 and 3, again assuming the \log_{10} titer values are normally distributed, MI will be used to create 100 complete data sets that will account for the random variability in the neutralizing titer values. Group 2 and 3 analyses will be performed separately, but using the same method. Baseline and Week 1 \log_{10} neutralizing titer values, stratification subgroup, year of birth, sex, and race will be used in the joint model to predict the \log_{10} neutralizing titer value for the primary estimand time point at Week 2. Qualitative tests for SARS-CoV-2 antibodies are required for inclusion in the trial and appropriate placement of subjects into their respective seronegative or seropositive groups. However, the chance for missing Baseline neutralizing titer values still exists. In addition, as the missing pattern of titer values may not be monotone, i.e., subjects may be missing Baseline neutralizing titer values, Week 1, or Week 2 neutralizing titer values, or a combination of these values, a FCS model will be used, assuming the existence of a joint distribution for all variables used to predict the missing values and allowing the Baseline and Week 1 \log_{10} titer results to be imputed, if needed, to inform the missing Week 2 neutralizing \log_{10} titer result.

For missing Baseline and Week 1 neutralizing titer values in Groups 2 and 3, titer results can still be assumed log-normally distributed. Using the FCS regression model, missing neutralization titer results will be imputed using the simulated from the posterior predictive distribution of the parameters Baseline and Week 1 \log_{10} neutralizing titers, stratification subgroup, year of birth, sex, and race.

After the creation of the 100 complete datasets, the fold-increase for Week 2 versus Baseline neutralizing titer results, i.e., the difference in the values on the \log_{10} scale, will be created for all Safety Analysis Set subjects. The mean difference in \log_{10} titers from Baseline to Week 2 and corresponding standard errors will be calculated within each imputation, and combined over the 100 imputations. The combined results will be presented on the \log_{10} scale using means and 95% CIs, as well as back transformed to present the geometric mean fold-increases and associated 95% CIs on the original scale.

As with Group 1, MI analyses will be performed in SAS using the PROC MI and PROC MIANALYZE procedures. A minimum of \log_{10} of half of the LLOQ will be set for imputed values to correspond to the observed data range. In addition, a seed of 19201 will be used for the procedure. The following is the sample code for the MI sensitivity analyses of the primary estimand for Groups 2 and 3.

titersl: the dataset containing the \log_{10} neutralizing titer data along with the covariates used in the analysis, one record per subject.

sex: The sex identifier

yob: Year of birth

race: The race identifier

stratgoup: Stratification subgroup (prior mRNA vaccine, prior Adenovirus-based vaccine, prior COVID-19 infection)

ltiterBL: Log₁₀ Baseline Titer Result

ltiterW1: Log₁₀ Week 1 Titer Result

ltiterW2: Log₁₀ Week 2 Titer Result

lfoldinc: Log₁₀ Fold Increase from Baseline to Week 2 Titer Result

```

proc mi data=titersl out=titermi n impute=100 seed=19201 minimum=[LLOQ/2];
  class stratgroup sex race;
  var stratgroup yob sex race ltiterBL ltiterW1;
  fcs nbiter=20 reg(ltiterW2 = ltiterBL ltiterW1 stratgroup yob sex race
    /details);
run;

data titersmi2;
  set titersmi;
  lfoldinc= ltiterW2 - ltiterBL;
run;

proc means data=titermi2 nointer nway;

```

```
by _imputation_;
var lfoldinc;
output out=summ(drop=_type_ _freq_) n=n mean=logmn stderr=logse;
run;

ods output parameterestimates=group2est;
proc mianalyze data=summ;
  modeleffects logmn;
  stderr logse;
run;
data group2est2;
  set group2est;
  GMFI=10**estimate;
  GMFI_LCL=10**LCLmean;
  GMFI_UCL=10**UCLMean;
  keep estimate lclmean uclmean GMFI:;
  label estimate='Mean Log10 Fold Increase'
    lclmean='Lower 95% CI of the Mean Log10 Fold Increase'
    uclmean='Upper 95% CI of the Mean Log10 Fold Increase'
    GMFI='Geometric Mean Fold Increase'
    GMFI_LCL='Lower 95% CI of the Geometric Mean Fold Increase'
    GMFI_UCL='Upper 95% CI of the Geometric Mean Fold Increase'
  ;
run;
```

